### 2.2 Trial Coordination / Monitoring

The study will appear in the following clinical trial registry: [clinicaltrials.gov](http://clinicaltrials.gov).

The Sponsor will enlist the support of PPD [REDACTED], a CRO, to conduct the clinical part of the study including study set-up, operation of an interactive web response system (IWRS) for randomization, coordination, monitoring, medical oversight, data capture, data management, statistical analysis, and clinical study reporting. The Sponsor will also make use of the CRO's central laboratory for sample analyses, storage, and shipment to specialized bioanalytical laboratories. The Sponsor will supervise all outsourced activities.

Investigational medicinal product (IMP) will be supplied by the Clinical Trial Supply Department of the Sponsor, and packaged, labeled and distributed by a designated contract manufacturing organization.

The Coordinating Investigator PPD [REDACTED] represents all Investigators for decisions and discussions regarding this study, consistent with the

International Council for Harmonisation (ICH) Topic E6 Good Clinical Practice (GCP); hereafter referred to as ICH GCP. The Coordinating Investigator will provide expert medical input and advice relating to study design and execution and is responsible for the review and signoff of the clinical study report (CSR). Signature pages for the protocol lead and the Coordinating Investigator as well as a list of Sponsor responsible persons are in [Appendix IV](#).

Subject enrollment and randomization will be managed by an IWRS.

Safety laboratory assessments will be performed centrally. Use of local laboratories is optional and to be used at the discretion of the Investigator; however, duplicate samples must also be collected and sent for central laboratory analysis. Only central laboratory data will be transferred into the clinical database. Unless otherwise specified (see Section 7.4.3), local laboratory results will not be recorded in the electronic case report forms (eCRFs). Urinalysis will be performed locally; microscopic analysis and urine protein to creatinine ratio (UPCR) will be performed centrally.

CCI

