The Global Drug Safety Department, Merck KGaA, Darmstadt, Germany, or their designated representatives will supervise drug safety and the timely reporting of adverse events (AEs), and serious adverse events (SAEs). Quality assurance of the study conduct will be performed by the Development Quality Assurance Department, Merck KGaA, Darmstadt, Germany.

The department of Global Biostatistics, Merck KGaA, Darmstadt, Germany, will supervise the statistical analyses, which will be outsourced to a CRO. Pharmacokinetic data analyses will be completed by Merck KGaA.

An independent data monitoring committee (IDMC) will be established to assess safety and tolerability of IMP during the conduct of the study and review the interim analysis (IA) if completed. The IDMC will be composed of a minimum of three members who do not have any conflict of interests with the study Sponsor, including two clinicians and a biostatistician. The full membership, mandate, and processes of the IDMC will be detailed in the IDMC charter. The IDMC will review the data from the interim futility analysis conducted by an independent third party statistician. Based on the pre-defined futility criteria, the IDMC will make recommendations to the Sponsor.

The IDMC will monitor the study until the last subject has either entered the LTE or completed the Safety Follow-Up Visit following the DBPC Treatment Period for subjects that did not rollover into the LTE, whichever occurs last. At that time, study monitoring may transition to an internal Safety Monitoring Committee (SMC). The SMC will review all available safety data on a regular basis during the open-label LTE. The SMC consists of Sponsor representatives (including, but not limited to, the Medical Responsible, the Drug Safety Product Lead, the biostatistician), the Medical Monitor from the CRO, and the Coordinating Investigator. The full membership, mandate, and processes of the SMC will be detailed in the SMC charter.

In addition, the trial will be advised and monitored by a Study Steering Committee. Details about this committee will be provided in a separate charter.

Details of structures and associated procedures will be defined in a separate Manual of Procedures, which will be prepared under the supervision of the Clinical Trial Leader.

CCI

CCI

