#### **Criteria for Withdrawal of Investigational Medical Product (Temporary and Permanent)**

The IMP should be temporarily withheld or permanently withdrawn if the following laboratory abnormalities occur or re-occur, as relevant, and re-initiation following temporarily withholding of IMP should be discussed with the Medical Monitor. If a subject's pre-dose baseline value is abnormal and/or falls within any of the below criteria, consult with the Medical Monitor regarding potential withdrawal, continued participation in study, and additional monitoring if needed. Retesting should be completed within 1 week:

- For a neutrophil count  $< 1000/\text{mm}^3$  (Grade 3 or 4) or platelet count  $< 50,000/\text{mm}^3$  (Grade 3 or 4), temporarily hold the IMP and recheck the value. If the value is still Grade 3 or 4, permanently discontinue the IMP; if the value improves to Grade 2, Grade 1 or is within normal limits, IMP may be reinitiated after discussion with the Medical Monitor. For a recheck value that decreases to Grade 2, perform repeat testing within 1 month.
- For a lymphocyte count  $< 200/\text{mm}^3$  (Grade 4), temporarily hold the IMP and recheck the value. If the value is still Grade 4, permanently discontinue the IMP; if the value improves to a Grade 3, discuss with the Medical Monitor; if the value improves to Grade 2, Grade 1 or is within normal limits, IMP may be reinitiated after discussion with the Medical Monitor. For a recheck value that improves to Grade 2, perform repeat testing within 1 month.
- For an increase in aspartate aminotransferase (AST) or alanine aminotransferase (ALT) to  $> 3 \times \text{ULN}$  (Grade 2 or higher), temporarily hold the IMP and recheck the value. If the value is still Grade 2 or higher, the IMP should be permanently withdrawn. The subject should be followed with additional testing as needed until a return to ULN or acceptable value as agreed upon by the Investigator and Medical Monitor. Consultations with specialists, such as a hepatologist, can be considered at the discretion of the Investigator and in conjunction with the Medical Monitor.
- For an increase in bilirubin to  $> 1.5 \times \text{ULN}$  (Grade 2 or higher), temporarily hold the IMP and recheck the value. If the value is still Grade 2 or higher, the IMP should be permanently withdrawn.

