- A comprehensive hepatic panel is requested for any subjects, for whom above AST or ALT withdrawal criteria are met and who permanently discontinue dosing due to elevated liver function tests. Subjects should be referred to a hepatologist who may recommend testing in addition to the following:
  - INR, PTT, fibrinogen, hsCRP
  - Hepatitis serology: anti-HAV IgG, anti-HAV IgM, HBsAg, anti-HBc, anti-HBsAg, anti-HCV, anti-HEV IgG and IgM, anti-VCA IgG and IgM, anti-EA IgG, anti-EBNA IgG, anti-CMV IgG and IgM
  - Antinuclear antibody, anti-smooth muscle antibody, and liver-kidney microsomal antibody
  - Albumin
- For an increase in amylase or lipase to  $> 2 \times$  ULN (Grade 3 or 4), temporarily hold the IMP and recheck the value. If the value is still Grade 3 or 4, permanently discontinue the IMP; if the value improves to Grade 2, Grade 1, or is within normal limits, IMP may be reinitiated after discussion with the Medical Monitor. For a recheck value that improves to Grade 2, perform repeat testing within 1 month.
- For an increase in serum creatinine to  $> 3 \times$  Baseline (Grade 3 or 4), temporarily hold the IMP and recheck the value. If the value is still a Grade 3 or 4, permanently discontinue the IMP.
- For an increase in serum creatinine  $> 1.5 \times$  Baseline to  $\leq 3 \times$  Baseline (Grade 2), temporarily hold the IMP and recheck the value. If the value is still Grade 2, discuss with the Medical Monitor; if the value improves to Grade 1 or is within normal limits, IMP may be reinitiated after discussion with the Medical Monitor.
- For any serum IgG level  $< 3$  g/L, temporarily hold the IMP and recheck the value. If the value is still  $< 3$  g/L, the IMP should be permanently withdrawn.
- For any increase in HBV DNA by PCR from negative/undetectable to detectable, and/or increase in HBV DNA by PCR from  $< 20$  IU/mL to  $\geq 20$  IU/mL, the IMP should be permanently withdrawn. The subject should be followed with additional testing and Hepatitis B treatment, as indicated per local guidelines, including consultation with a specialist, such as a hepatologist, at the discretion of the Investigator and in conjunction with the Medical Monitor.
- For any other laboratory abnormality of Grade 4 severity, temporarily hold the IMP and recheck the value. If the value is still a Grade 4, the IMP should be permanently withdrawn. If the retest value improves, discuss with the Medical Monitor.

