## 6.10 Blinding

Treatment with M2951 and placebo will be double-blinded. Subjects, Investigators, study staff and the study teams (Sponsor and PPD ) will be blinded to treatment. All breaks of the study blind must be adequately documented.

Packaging and labeling will be prepared to protect the blinded nature of the study. IMP (M2951 or placebo) will not be distinguishable from each other and will be covered by suitable labels to prevent subjects and study personnel from noticing any differences in the tablets of M2951 versus placebo. Blinded treatment kit numbers will be obtained through the IWRS as described in Section 6.3.

After Day 1, results of analyses that could reveal the PD effects of M2951 in an individual subject will be blinded to the study site, the Sponsor, and the CRO. These analyses will include: total Ig (IgA, IgM, and IgG), IgG subclasses, C3, C4, anti-dsDNA, ANA, other autoantibodies (anticardiolipin, anti-Smith antibody [anti-Sm]; an antibody to ribonucleoproteins; and antinuclear antibodies associated with autoimmune diseases including Sjögren syndrome and SLE [anti-Ro, anti-La]), and cell counts by flow cytometry (total B cells and B cell subsets). If the Investigator considers it necessary to have any of the above results for acute medical management of the subject after Day 1, then this should be discussed with the Medical Monitor. It should be noted that in the clinical utility of monitoring anti-dsDNA levels may be diminished due to an anticipated drop in levels as a consequence of M2951's PD effects. Lymphocyte counts as assessed by routine complete blood counts will not be blinded, as these results are not anticipated to reveal PD effects, since B lymphocytes represent a small proportion of total lymphocytes (5% - 20%).

An IA for futility may be triggered when 100% of the planned enrollment required for the primary analysis reaches 24 weeks of treatment, or discontinues treatment prematurely prior to Week 24. The IDMC will be fully unblinded to treatment and will make a recommendation, as described in the IDMC charter. A limited set of endpoints will be analyzed for the IA, including Week 24 SRI-4 response for the whole study population and Week 24 SRI-6 response for the HDA subgroup.

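### Sections 5.5.2 and 6.10 do not fit together: the IgG < 3 g/L stopping rule must be applied by people blinded to IgG, and neither section visibly says how they learn that the limit was crossed

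*Protocol*

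**What the plan says.** **The stopping rule.** Section 5.5.2, under the criteria for temporary and permanent withdrawal of study drug, gives IgG its own rule. It opens "For any serum IgG level", sets the limit at below 3 g/L, and continues "g/L, temporarily hold the IMP and recheck the value". If the second value is still below 3, the rule ends "g/L, the IMP should be permanently withdrawn". The introduction to the list adds "Retesting should be completed within 1 week" and has any restart after a hold discussed with the Medical Monitor. Section 6.5.4.1 only points back to section 5.5.2.

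**The blind.** Section 6.10 lists the results withheld after Day 1, which "will be blinded to the study site, the Sponsor, and the CRO. These analyses will include: total Ig (IgA, IgM, and IgG" and go on to IgG subclasses, C3, C4, autoantibodies and flow-cytometry cell counts. The one exemption in that paragraph is for routine lymphocyte counts. The one release route begins "If the Investigator considers it necessary to have any of the above results for acute medical management of the subject after Day 1" and then calls for a discussion with the Medical Monitor.

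**Who the parties are.** Section 2.2, in describing the committee for the extension, names "the Medical Monitor from the CRO". The same section assigns medical oversight to the CRO, uses the CRO's central laboratory for sample analysis, and says "Use of local laboratories is optional and to be used at the discretion of the Investigator".

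**The concern.** A mandatory threshold rule protects subjects only if someone who can act sees the threshold crossed. Here the site, which must hold the drug and order the recheck, and the Medical Monitor, who must be consulted on restart, both belong to groups that section 6.10 blinds to the value. A low IgG may cause no symptoms, so a release route that starts with clinical need may never be used.

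The protocol itself treats the measurement as relevant to safety. Section 7.4.3.1.1 says that immunoglobulin levels may change through the drug's mechanism and are collected as a safety evaluation. Section 8.3.1 makes them part of the primary safety endpoints. Section 3.1 lists infection among the important potential risks. If the unseen documents contain no alert, a subject could meet the stopping criterion and stay on treatment. If they do contain one, a site following sections 5.5.2 and 6.10 is still not told how the information will reach it.

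**Working it through.** **Step 1. Set the rule against the blind.**

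| What 5.5.2 requires | Who must do it | What 6.10 gives them after Day 1 |
|---|---|---|
| Recognise IgG < 3 g/L and hold drug | Site | Blinded to total IgG |
| Obtain a recheck within 1 week | Site | Not told the first value |
| Discuss restart after the hold | Site with the Medical Monitor (CRO) | Site and CRO both blinded |
| Stop permanently if still < 3 g/L | Site | The recheck is also a total IgG result after Day 1 |

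Section 5.5.2 gives separate rules for neutrophils, platelets, lymphocytes, AST/ALT, bilirubin, amylase/lipase, creatinine, IgG and HBV DNA. IgG is the only one of these on the blinded list. Lymphocytes are expressly left unblinded, although the reason given is that they are not expected to reveal pharmacodynamic effects.

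**Step 2. Look for another visible route to the person who must act.**

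- *Release on request (6.10).* It starts with the Investigator thinking the result necessary, so it needs prior suspicion.
- *Local testing (2.2 and 7.4.3).* It is at the Investigator's discretion or requested by the study team, and is not linked to the IgG rule.
- *Routine chemistry (Table 11).* A footnote says total immunoglobulins are measured only where Table 1 specifies, not as a standard evaluation. Total protein and albumin are not on the blinded list and could hint at a fall, but section 5.5.2 ties neither to IgG.
- *IDMC (3.1, 6.11).* It is not among the blinded parties and reviews safety data continually, but no IgG trigger for a single subject is stated. The text in section 6.11 concerns unblinding treatment assignment after a serious event.

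None of these is a routine route for a low value without symptoms.

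**Step 3. Bound the size.** No frequency of IgG < 3 g/L is given, so the number affected cannot be estimated.

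*Fall needed.* Section 5.3.2 excludes a Screening IgG below 6 g/L. From that floor, (6 − 3)/6 = 50%, so the fall must exceed 50%, and more for anyone who starts higher.

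*Longest possible further dosing in the double-blind period.* Table 1 schedules immunoglobulin draws at Weeks 2, 4, 12, 24 and 36 before the end of treatment on Day 365. Remaining weeks = (365 − trial day)/7:

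| Draw | Trial day | Remaining weeks |
|---|---|---|
| Week 2 | 15 | 350/7 = 50 |
| Week 4 | 29 | 336/7 = 48 |
| Week 12 | 85 | 280/7 = 40 |
| Week 24 | 169 | 196/7 = 28 |
| Week 36 | 253 | 112/7 = 16 |

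These are worst cases. They assume no laboratory alert, no IDMC action, no Investigator request and no other reason to stop.

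**The case against.** The strongest reply is that the argument rests on missing text where text has been removed. All of section 7.5 and the end of section 6.10 are redacted. The list of changes in Appendix V says the blinded list in section 6.10 was aligned with section 7.5.2, so a hidden section covers the same tests and is a natural place for an alert. The laboratory manual, Manual of Procedures and IDMC charter are not shown either. A reader might infer from the visible text that no alert exists. The documents do not support that, and the point does not claim it.

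Second, a threshold rule and blinded values can coexist. Section 5.5.2 says what to do when IgG is low, not that the site must see every value. The central laboratory belongs to the CRO and necessarily holds the result, so the blind cannot literally cover everyone there. A laboratory alert would be compatible with both sections. This stands: what is missing is a stated notification step, and the two rules are not irreconcilable.

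Third, the consequence is easily exaggerated. A reader might take the 16 to 50 weeks as expected exposure below the limit; they are outer bounds. Nor do the long gaps between scheduled draws show that the one-week recheck fails, because a recheck is an unscheduled test. The Investigator's request route and the IDMC's review make prolonged exposure less likely. No efficacy analysis, power or error rate is affected.

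What survives is narrow. The 6.10 paragraph that sets the blind, the exemption and the release route is unredacted, as is the IgG rule in section 5.5.2, and neither refers to an alert.

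**Conclusion.** The inconsistency holds for the double-blind period. A site following sections 5.5.2 and 6.10 exactly as written could not apply a mandatory stopping rule to a subject whose IgG fell below 3 g/L without clinical suspicion.

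The conclusion rests on two readings of the visible text: that the Medical Monitor falls under the blind on the CRO, and that no exception appears in the two sections concerned. It does not extend to saying that the trial lacks an alert or that any subject will be dosed below the limit. The event is probably uncommon given the fall required, but its frequency is unknown. Severity is minor if a procedure exists elsewhere and only the cross-reference is missing, and should-fix if it does not.

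**What to change.** Add one or two sentences to both sections 6.10 and 5.5.2. When a total IgG result after Day 1 is below 3 g/L, the central laboratory, or an existing unblinded party such as the IDMC's statistician, sends the site and the Medical Monitor an alert saying only that the limit has been crossed. After the recheck it reports only whether the value is still below 3 g/L. All other immunoglobulin values stay blinded. If such a procedure is already in section 7.5.2, the laboratory manual or the IDMC charter, a cross-reference in both sections is enough. The limit itself is a matter for the clinical team and need not change.

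The cost is setting up a laboratory flag and a small text amendment, or the amendment alone. The downside is occasional partial unblinding, because an alert hints at active treatment. It is confined to subjects who cross the limit, and those whose low value is confirmed must stop study drug anyway.

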## 6.11 Emergency Unblinding

The Investigator will have the ability to break the blind with regard to IMP for any subject at any time through the IWRS. However, the Investigator should make every effort to contact the responsible Medical Monitor or their designee to discuss the subject's emergency situation and the need to unblind prior to unblinding any subject and must contact the Sponsor or designee within 1 working day after the event occurs without revealing to the Sponsor personnel the result of the code break. The Investigator will be able to access the subject's treatment assignment 24 hours a day through the IWRS using a unique access code and user number (different from those used to assign subjects to treatment through the IWRS). Should the IWRS be unavailable for any reason, the Investigator will be able to break the blind via a telephone call to the IWRS help desk, which is available 24 hours a day. The help desk can access the database manually to perform the unblinding via telephone in the event that the IWRS is not operational. The Investigator must record the date of unblinding and the reason in the eCRF. Contact information for breaking the blind in an emergency is given on the subject emergency card provided to each subject (see Section 9.4).

Under certain circumstances, the IDMC or Drug Safety may be required to unblind the treatment assignment for an individual subject following a SAE or other serious event; (e.g., if an expedited

regulatory report is required). See Section 7.4.1.4 for further details on expedited reporting and SAEs.

### 6.11.1 Unblinding for Regulatory Authorities

In cases where unblinding is required for the purposes of reporting expedited safety events to country-specific regulatory agencies or IECs, the unblinding will be performed by an authorized person(s). A blinded version of any documents to be submitted to the authorities will be shared as appropriate with study staff and site personnel. Only the authorized person(s) within the CRO and regulatory affairs will have access to the unblinded version of any documents. The procedures for requesting and obtaining unblinded information and for maintaining the integrity of the data and clinical study are outlined in the pharmacovigilance plan for this study.

### 6.12 Treatment of Overdose

An overdose is defined as any dose greater than the highest total daily dose included in a CTP or planned for an individual subject enrolled in the study. CCI

. Any overdose must be recorded in the study medication section of the eCRF.

For monitoring purposes, any case of overdose – whether or not associated with an AE (serious or nonserious) – must be reported to the Sponsor’s Global Drug Safety department or designee in an expedited manner using the appropriate reporting form (see Section 7.4).

The effects of an overdose of M2951 are unknown, and there is no known specific treatment in case of overdose. In the event of overdose, subjects should be considered for hospitalization for observation if clinically indicated, and the Investigator or treating physician should use appropriate clinical judgment for the management of any clinical or investigational findings.

### 6.13 Medical Care of Subjects after End of Trial

After a subject has completed the study or has withdrawn early, the subject is free to access further treatment as deemed appropriate by the Treating Investigator. The Sponsor will not provide any additional care to subjects after they leave the study because such care should not differ from what is normally SoC for subjects with SLE.

## 7 Trial Procedures and Assessments

Prior to performing any study assessments not part of the subject’s routine medical care, the Investigator will ensure that the subject has provided written informed consent according to the procedure described in Section 9.2.

Upon subject’s agreement, the subject’s primary health care provider can be informed about subject’s enrollment in the study.

Throughout the study, subjects will undergo the assessments detailed in [Table 1](#) and [Table 2](#), including collection of patient-reported HRQoL data and blood sampling.

HRQoL and subject self-assessment questionnaires must be completed first at visits where these assessments are collected.

Unscheduled visits may occur at any time during the study in case of suspected flares or AEs (assessments to be performed according to the Investigator's judgement).

